3.4. DESCRIPTION OF TRIAL DESIGN

This is a Phase 3, multicenter, double-masked, randomized, placebo-controlled, parallel-group study designed to evaluate the safety and efficacy of KPI-121 1.0% ophthalmic suspension versus placebo in subjects who require treatment of postoperative anterior ocular inflammation. Approximately 720 subjects who are candidates for cataract surgery will be screened and approximately 500 subjects who, after undergoing routine, uncomplicated cataract surgery, present at Visit 3 (Day 1) with \geq 2 anterior chamber cells in the study eye will be randomized in this study at approximately 35 centers located in the US.

Subjects who experience postoperative inflammation on the first day following routine, uncomplicated, cataract surgery and who meet all other eligibility criteria will be randomized to one of two study groups in an approximate 1:1 ratio:

- KPI-121 1.0% ophthalmic suspension, BID
- Placebo, BID

Dosing of investigational product will be initiated on the day following surgery, instilled as 1-2 drops in the study eye BID for 14 ± 1 days. The first dose of investigational product will be administered by the subject under the supervision of a designated study team member who is otherwise uninvolved in the assessment or evaluation of the subject. Except for this investigational product administration, no other information or discussion regarding the subject's assigned investigational product will be exchanged, in order to maintain the masking for this trial.

This study will include up to 7 clinic visits (including the surgery day) over 18 to 33 days total study duration. Visit 1 (Screening) will occur between 14 to 1 day(s) prior to surgery and subjects who meet preoperative screening inclusion/exclusion criteria will be entered into the study. At Visit 2 (Surgery/Day 0), subjects will undergo routine cataract surgery according to the Investigator's normal procedures. Visit 3 (Randomization/Day 1) will occur on the day following surgery. Subjects who meet the qualifying postoperative randomization criteria will be eligible for randomization to one of the two study groups and will initiate dosing with investigational product on that day. Following randomization, subjects will be instructed to instill investigational product in the study eye two times a day (BID) for 14 ± 1 days, up until

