4.3. RANDOMIZATION CRITERIA

To qualify for randomization at Visit 3 (Postoperative Day 1), a subject must:

- 1. Have undergone routine, uncomplicated cataract surgery (e.g., phacoemulsification with posterior chamber IOL implantation, not combined with any other surgery).
- 2. Have \geq Grade 2 anterior chamber cells.
- 3. Continue to meet inclusion/exclusion criteria with respect to current ocular and medical conditions (Section 4.1 and Section 4.2), and must not have taken prohibited medications (Section 6.2.2).

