5.1.3. Visit 3: Randomization Visit (Day 1)

The randomization visit will occur 1 day after Visit 2/Surgery Visit. This visit should be scheduled in the morning (if possible) to allow for administration of two doses of investigational product during the day for eligible subjects.

Eligible subjects who meet the randomization criteria (Section 4.3) will continue in the study.

The following will be performed/assessed (**NOTE:** All ocular assessments must be performed in both eyes):

- Obtain Subject-Rated Ocular Pain Assessment
- Review use of any concomitant medications since the last visit
- Assess occurrence of any AEs since the last visit (**NOTE**: Expected changes or the presence of inflammation resulting from routine uncomplicated cataract surgery will not be captured as AEs.)
- Perform:
 - Snellen Distance VA by pinhole method
 - o Slit Lamp Biomicroscopy

CONFIDENTIAL

- Signs of anterior ocular inflammation (cell and flare grading)
- Palpebral conjunctival erythema, corneal edema, hyphema, ciliary flush, bulbar conjunctival injection
- IOP Measurement

Upon verification of study eligibility (Section 4.3), eligible subjects will be randomized to receive either KPI-121 1.0% ophthalmic suspension dosed BID or placebo dosed BID. The following will be performed for all randomized subjects:

- Administer the first dose of double-masked investigational product in the clinic under the supervision of designated study personnel.
- Prior to administration of investigational product, remind the subjects regarding the proper method for instillation including but not limited to shaking investigational product bottle prior to each instillation.
- Since subjects will receive one dose of investigational product in the clinic, instruct the subject to self-administer one additional dose of investigational product on the first day.
- Assess the occurrence of any AEs after investigational product administration
- Dispense investigational product kits and instructions for administration
- Schedule subjects to return for Visit 4 on Day 4 ± 1 day.

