9.1.2. Analysis of Efficacy

The primary analysis population will be the Intent-to-Treat (ITT) population, defined as all subjects randomized. A subset of efficacy analyses will be repeated using data from those subjects who were randomized, completed 14 days of study product use, had complete data at Visit 5 (Day 8 ± 1 day) and did not have significant protocol deviations, the Efficacy Evaluable (EE) population. Rescued subjects will be included in the EE population if they did not have significant protocol deviations.

The primary analysis of all ophthalmic efficacy measures will be based on a single study eye for each subject. Each subject's study eye will be defined as the surgery eye. The set of primary endpoints, using hierarchical statistical testing, is (1) proportion of study eyes with complete resolution of anterior chamber cells (grade = 0) at postoperative Visit 5 (Day 8 ± 1 day) maintained through Visit 6 (Day 15 ± 1 day) without receiving rescue medication prior to Visit 6 (Day 15 ± 1 day) as compared between KPI-121 1.0% ophthalmic suspension and placebo, and (2) proportion of study eyes with complete resolution of pain (grade = 0) at postoperative Visit 5 (Day 8 ± 1 day) maintained through Visit 6 (Day 15 ± 1 day) without receiving rescue medication prior to Visit 6 (Day 15 ± 1 day) as compared between KPI-121 1.0% ophthalmic suspension and placebo.

The following scoring scale for anterior chamber cells will be used:

0 = No cells seen

1 = 1 - 5 cells

2 = 6 - 15 cells

3 = 16 - 30 cells

4 =greater than 30 cells

The following scoring scale for ocular pain will be used:

- 0 = None
- 1 = Minimal
- 2 = Mild
- 3 = Moderate
- 4 = Moderately Severe
- 5 = Severe

Using the hierarchical testing scheme, the first test will be the proportion of study eyes with complete resolution of anterior chamber cells (grade = 0) at Visit 5 (Day 8 ± 1 day) maintained through Visit 6 (Day 15 ± 1 day) without receiving rescue medication prior to Visit 6 (Day 15 ± 1 day) as compared between KPI-121 1.0% ophthalmic suspension dosed BID and placebo dosed BID using the χ^2 statistic.

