9.2. SAMPLE SIZE ESTIMATION

A two group χ^2 test with a 0.05 two-sided significance level will have 99% power to detect the difference between a proportion with complete resolution of anterior chamber cells in the active group of 0.31 and the placebo group proportion of 0.15 when the sample size in each group is 250. The power is the same for the complete resolution of pain endpoint.

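### The anterior chamber cell primary is tested by a valid but unadjusted chi-square; stratifying by the Visit 3 cell grade, already recorded before randomization, is a nearly free improvement.

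*Combined protocol and SAP*

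**What the plan says.** **Test.** Section 9.1.2 puts cells first in the hierarchy: "Using the hierarchical testing scheme, the first test will be the proportion of study eyes with complete resolution of anterior chamber cells". The comparison is between KPI-121 and "placebo dosed BID using the χ^2 statistic". No covariate, stratum or adjusted supporting analysis is named. Pain is tested only if the cell result is significant in favour of KPI-121, and that step names its test only by referring back to the one used for cells.

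**Baseline.** Section 4.3 requires at least "Grade 2 anterior chamber cells" for randomization. On the 0-4 scale this admits grade 2 (6-15 cells), grade 3 (16-30) and grade 4 (more than 30). The Visit 3 procedures in Section 5.1.3 include slit lamp grading, listed as "Signs of anterior ocular inflammation (cell and flare grading". Eligibility is verified after that, and randomization and the first dose follow.

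**Randomization.** Section 3.4 says that subjects are "randomized to one of two study groups in an approximate 1:1 ratio". Sections 3.4.2 and 6.5 describe how the code is generated and kept, and mention no stratification.

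**Supporting analyses.** Those described are a repeat in the efficacy evaluable population (Sections 9.1.2 and 9.6) and a tipping point analysis if more than 5% of Day 8 data are missing in an arm (Section 9.4). Section 9.3 makes every other p-value descriptive.

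**The concern.** The endpoint is grade 0 at Day 8, held to Day 15 without rescue. The Visit 3 grade is the same measurement on the same scale about a week before that Day 8 reading. An eye that starts above 30 cells can reasonably be expected to clear less often than one that starts at 6-15, although the documents do not say so. The plan uses this baseline elsewhere: the third secondary endpoint is a change from it. The test that opens the hierarchy does not.

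Two things are at stake. One is precision: if grade is prognostic, the unadjusted test gives up some power. The other is how well the result stands up in the one trial that is run. If the arms happen to differ in starting grade, a reader will ask whether the result reflects that difference. An adjusted test chosen after unmasking would be descriptive only under Section 9.3, so it could neither confirm a win nor recover a loss.

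**Working it through.** **1. The plan's own figure.** Section 9.2 states a "test with a 0.05 two-sided significance level will have 99% power to detect the difference", with "complete resolution of anterior chamber cells in the active group of 0.31 and the placebo group proportion of 0.15" and "when the sample size in each group is 250".

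- Pooled rate (0.31 + 0.15)/2 = 0.23; null SE = √(2 × 0.23 × 0.77/250) = 0.0376; 1.96 × 0.0376 = 0.0738.
- Alternative SE = √((0.31 × 0.69 + 0.15 × 0.85)/250) = 0.0370.
- Power = Φ((0.16 − 0.0738)/0.0370) = Φ(2.33) = 99.0%.

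The stated 99% reproduces (99.02%, without continuity correction).

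**2. A smaller effect, 25% v 15%.** Null SE = √(2 × 0.20 × 0.80/250) = 0.0358; alternative SE = √((0.25 × 0.75 + 0.15 × 0.85)/250) = 0.0355. Power = Φ((0.10 − 0.0701)/0.0355) = Φ(0.84) = 80.0%.

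**3. Assumptions needed to compare the tests.** None of these is in the documents. Visit 3 grades 2/3/4 in shares of 60/30/10%; a common odds ratio for treatment; 250 per arm; and three strengths of dependence on grade, each averaging 15% on placebo (for example 0.6 × 20 + 0.3 × 9 + 0.1 × 3 = 15).

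| Dependence | Placebo clearing, grades 2/3/4 | CMH power, 25% v 15% (chi-square about 80%) | Information gain |
|---|---|---|---|
| Weak | 17 / 13 / 9% | 80.5% | about 0.6% |
| Moderate | 20 / 9 / 3% | 81.9% | about 4% |
| Strong | 22.5 / 4.5 / 1.5% | 83.5% | about 9% |

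Simulated chi-square power at 25% v 15% runs between 80.0% and about 80.5%, so the gain is about 0.2 point (80.5 − 80.3) to 3.5 points (83.5 − 80.0). In subjects, the information gains are worth 500 × 0.006 = 3, 500 × 0.04 = 20 and 500 × 0.09 = 45. At the planned 31% v 15%, the chi-square has 99.1% and CMH 99.1 to 99.5%.

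**4. A chance imbalance, with no treatment effect.** The SD of the difference between arms in grade 2 share is √(2 × 0.6 × 0.4/250) = 4.4 points, so 2 SD is 8.8 points. The null SE of the difference in clearing is √(2 × 0.15 × 0.85/250) = 3.2 points.

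- Moderate case: grades 3 and 4 together clear at (0.3 × 9 + 0.1 × 3)/0.4 = 7.5%, against 20% in grade 2, a gap of 12.5 points.
- Shift = 0.088 × 12.5 = 1.1 points, or 1.1/3.2 = 0.34 SE.
- One-sided rate = P(Z > 1.96 − 0.34) = about 5% if the imbalance favours active, and P(Z > 1.96 + 0.34) = about 1% if it favours placebo.

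Simulation for a 2-SD imbalance favouring active gives 3.3%, 5.1% and 7.0% (weak, moderate, strong) for the chi-square, and about 2.2 to 2.6% for CMH. At 1 SD the chi-square rates are 2.9%, 3.6% and 4.1%.

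**5. A second set of assumptions.** Grade mixes of 60/30/10, 40/40/20 and 33/34/33%, with the odds of clearing divided by 1, 1.5, 2 or 3 per grade step.

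- Power at 31% v 15%: 99.0-99.2% unadjusted, 99.0-99.5% stratified.
- Two-sided type I error over all randomizations: 4.9-5.1% unadjusted, 4.8-5.1% stratified.
- Where grade is prognostic (1.5 to 3 per step), imbalance shifts the expected difference by no more than 0.5-1.8 points in 95% of trials.
- In the 5% of those trials whose imbalance most favours active, the one-sided rate is 3.4-7.7% unadjusted and 2.2-2.6% stratified.
- With no dependence on grade, the two tests have the same power to within simulation error.

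**The case against.** The strongest reply is that nothing here is wrong. Randomizing about 500 eyes 1:1 is itself protection against imbalance, and the 5% level of the chi-square already allows for what remains. The 3 to 7% rates describe one tail: an imbalance of 2 SD or more towards active has a probability of about 2.3%, its mirror image is equally likely, and over all randomizations the rate averages 2.5%. At the planned effect the gain in power is half a point at best. The larger gains need a 10-point effect that the plan does not assume, and a strong dependence on grade. The strong case implies odds of clearing about 6 times higher in grade 2 than in grade 3 (0.225/0.775 against 0.045/0.955), and nothing supplied says that this case applies.

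All of this stands, and it rules out several readings that a reader might otherwise reach: that the test is biased or its error rate inflated, that the design leaves the comparison unprotected, or that power is lost whenever the effect is smaller than planned. The last is true only if grade is prognostic.

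It could also be argued that an adjusted sensitivity analysis would be enough. That would help interpretation, but under Section 9.3 it would be descriptive and would leave the power unused. Finally, Section 9.5 mentions a statistical analysis plan, while the statistical text supplied is the protocol's Section 9; this point applies to that text.

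**Conclusion.** This is a worthwhile improvement and not an error. The documents establish that the gatekeeping test is unadjusted, that the grade is on file before randomization, and that no stratification is described. They do not establish how strongly grade predicts clearing, so every figure for the gain is conditional on assumption: at most about 0.5 point of power at 31% v 15%, about 0.2 to 3.5 points at 25% v 15%, and a conditional false-positive rate held near 2.5% where the chi-square's would be about 3 to 7% after a 2-SD imbalance towards active. If grade is not prognostic, the two tests give almost the same answer, so little is risked by stratifying.

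A reader might infer that a chance imbalance could invalidate the trial's main result. The documents and the calculations do not support that: the overall level stays at about 5%, and the likely shift of 0.5-1.8 points is small beside a planned difference of 16.

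The strata depend on a point that the protocol leaves open. Section 4.3 sets entry by grade. The Synopsis (Study Design) and Sections 1.4 and 3.4 set it at 2 or more cells without the word grade, and read literally that would admit an eye with 2-5 cells, which is grade 1.

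**What to change.** Before unmasking, in Section 9.1.2:

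- Replace the chi-square for primary endpoint 1 with a Cochran-Mantel-Haenszel test stratified by Visit 3 study-eye cell grade, at two-sided 0.05.
- Report the Mantel-Haenszel risk difference with its 95% CI.
- Keep the unadjusted chi-square as a named sensitivity analysis.
- Name the pain test explicitly, because the present cross-reference would otherwise carry the new cell test over to pain.
- Define the strata by the recorded grades (2, 3 and 4 under Section 4.3), and state a rule for any randomized eye recorded below grade 2.

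Reconcile Section 4.3 with the cell-count wording in the Synopsis, Section 1.4 and Section 3.4.

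The power figure in Section 9.2 can stand; the calculations above show the stratified test doing as well or slightly better. The cost is a few lines of text and a slightly less simple test, with what may be a small grade 4 stratum that CMH can handle. No new data, visits or subjects are needed.

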If this test is statistically significant at the two-sided $\alpha = 0.05$ level in favor of the KPI-121 1.0% ophthalmic suspension group, then the difference in the proportion of study eyes with complete resolution of pain (grade = 0) at Visit 5 (Day 8 ± 1 day) maintained through Visit 6 (Day 15 ± 1 day) without receiving rescue medication prior to Visit 6 (Day 15 ± 1 day) as compared between KPI-121 1.0% ophthalmic suspension dosed BID and placebo dosed BID will be tested using the same statistic.

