12. ETHICS

12.1. Institutional Review Board

This protocol and the informed consent form must be approved by an appropriately constituted and qualified IRB and the approvals made available to the sponsor or designee prior to the start of enrollment into the study. Materials used to recruit subjects will be approved by the appropriate IRB and the approvals made available to the sponsor or designee prior to their use. In addition, the Investigator's Brochure should be submitted to the IRB. Written IRB approval must adequately identify the protocol and informed consent form. Copies of all approved materials, all correspondence with the IRB, and written approval from the IRB must be made available to the sponsor (or designated monitor).

Any modification of study procedures or amendments to the protocol must be approved by the IRB prior to implementation. In the event that a modification or amendment is considered by the Investigator to be immediately necessary to ensure subject safety, the Investigator will promptly notify his or her IRB and the sponsor.

Investigators will report all SAEs reported at their site to their IRB, as appropriate.

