APPENDIX 2: SUBJECT-RATED OCULAR PAIN ASSESSMENT

In the clinic, subjects will be handed a laminated card on which is printed the Subject-Rated Ocular Pain Assessment. Each subject will be asked to subjectively rate their pain at Visit 3 to 7 based on this scale. This information will be provided to study personnel to enter into the subject's source documentation. The grading scale for pain to be used will be as follows:

0 = None: Absence of positive sensation.

1 = Minimal: Presence of mild sensation or discomfort typical of postoperative

surgery (e.g., diffuse or focal foreign body sensation, mild transient

burning or stinging, etc.)

2 = Mild: Mild, tolerable aching of the eye.

3 = Moderate: Moderate or more prolonged aching sufficient to require the use of

over the counter (OTC) analgesics (e.g. acetaminophen).

4 = Moderately Severe: More prolonged aching requiring the use of an OTC analgesic

other than acetaminophen.

5 = Severe: Intense ocular, periocular or radiating pain (e.g. constant or nearly

constant sharp stabbing pain, throbbing or aching, etc.) requiring

prescription analgesics.

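### The pain primary is tested by a plain chi-square that ignores the pre-dose pain grade, although eyes already at grade 0 can enter and count as resolved. Stratifying by that grade is valid and costs no material power.

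*Combined protocol and SAP*

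**What the plan says.** Section 9.1.2 tests the two primaries in sequence. Cells come first, "as compared between KPI-121 1.0% ophthalmic suspension dosed BID and placebo dosed BID using the χ^2 statistic". If that is significant in favour of active treatment, the pain proportion "as compared between KPI-121 1.0% ophthalmic suspension dosed BID and placebo dosed BID will be tested using the same statistic". No stratum or covariate is named for either test.

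The pain grade exists before treatment. In Section 5.1.3, "Obtain Subject-Rated Ocular Pain Assessment" is the first Visit 3 assessment listed, and randomization and the first dose follow the eligibility check. Appendix 2 confirms the schedule: "Each subject will be asked to subjectively rate their pain at Visit 3 to 7 based on this scale". The scale runs from 0 (none) to 5 (severe).

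Section 4.3 sets a floor for inflammation, at least "Grade 2 anterior chamber cells", and none for pain. Section 3.1 defines pain success as a state: grade 0 at Visit 5, maintained through Visit 6, with no rescue before Visit 6. No fall from the Visit 3 grade is required.

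Section 9.2 gives power for cells at 0.31 v 0.15 with 250 per group, then adds: "The power is the same for the complete resolution of pain endpoint". It gives no pain rates.

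**The concern.** The two primaries differ in a way that the shared test overlooks. No eye can enter with cells already at grade 0. An eye can enter with pain at grade 0, and it then succeeds simply by staying there. The Visit 3 pain grade is thus a natural candidate for a strong baseline predictor of the pain endpoint. It is collected on schedule but left out of the test.

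Error control is not in question, since randomization balances pain-free eyes between arms in expectation. What is at stake is power for a primary endpoint. Section 9.2 does not show how the stated 99% would survive if pain-free entrants raised the placebo rate or reduced the average effect.

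**Working it through.** **1. The plan's own figure.** Inputs from Section 9.2: 0.31 v 0.15, 250 per group, two-sided 0.05. With the pooled variance under the null:

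- Pooled rate = (0.31 + 0.15)/2 = 0.23.
- SE under the null = √(2 × 0.23 × 0.77/250) = 0.0376.
- SE under the alternative = √((0.31 × 0.69 + 0.15 × 0.85)/250) = 0.0370.
- Power = Φ((0.16 − 1.96 × 0.0376)/0.0370) = 0.990. The stated 99% is reproduced.

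For pain it carries over only if the rates suit. By the same formula, a 16-point difference at a placebo rate of 0.30, 0.40 or 0.50 gives 96.0%, 95.0% or 95.4%.

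**2. What stratifying removes.** Let f be the pain-free share and δ the difference in response rate between pain-free and other eyes within an arm. Each arm's variance contains f(1 − f)δ², which stratification takes out. Example (assumed): f = 0.3, placebo 0.55 in pain-free and 0.20 in other eyes, +16 points in both.

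- Overall rates: placebo 0.305, active 0.465.
- Sum of variances = 0.305 × 0.695 + 0.465 × 0.535 = 0.461.
- Removed = 2 × 0.3 × 0.7 × 0.35² = 0.051, or 11%.

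Over f = 0.2 to 0.4 the share removed is 0% if the grade is not prognostic, 3–4% for 0.45 v 0.25, 9–12% for 0.55 v 0.20, and 22–30% for 0.70 v 0.15.

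**3. Simulated power of the pain test on its own.** All pain rates are assumptions. Settings: 250 per arm, 200,000 trials per case, two strata, no continuity correction, success = two-sided p < 0.05 in favour of active. Each cell shows 20/30/40% of eyes pain-free.

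| Effect, pain-free / other eyes | Placebo rate, pain-free v other | Chi-square, % | CMH, % | Gain, points |
|---|---|---|---|---|
| +16 / +16 | 0.30 v 0.30 | 95.9/95.8/95.8 | 95.9/95.9/95.9 | 0.0/0.1/0.1 |
| +16 / +16 | 0.45 v 0.25 | 96.0/95.8/95.6 | 96.5/96.4/96.2 | 0.5/0.6/0.6 |
| +16 / +16 | 0.55 v 0.20 | 96.6/95.8/95.5 | 97.7/97.5/97.3 | 1.1/1.7/1.8 |
| +16 / +16 | 0.70 v 0.15 | 96.8/95.7/95.4 | 99.1/99.1/99.1 | 2.3/3.4/3.7 |
| +8 / +16 | 0.45 v 0.25 | 92.0/88.1/83.4 | 92.5/89.0/84.4 | 0.5/0.9/1.0 |
| +8 / +16 | 0.55 v 0.20 | 92.7/88.3/83.4 | 94.3/91.1/86.9 | 1.6/2.8/3.5 |
| +8 / +16 | 0.75 v 0.15 | 92.7/87.5/82.7 | 97.3/95.7/93.4 | 4.6/8.2/10.7 |
| 0 / +16 | 0.45 v 0.25 | 85.2/73.9/59.7 | 85.6/74.7/60.6 | 0.4/0.8/0.9 |
| 0 / +16 | 0.55 v 0.20 | 86.2/74.3/59.5 | 88.0/77.2/63.1 | 1.8/2.9/3.6 |
| 0 / +16 | 0.75 v 0.15 | 86.2/72.7/59.1 | 92.7/84.3/71.7 | 6.5/11.6/12.6 |

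The 0.75 v 0.15 rows are an extreme contrast. In the last three rows the overall difference is 16 × (1 − f) = 12.8/11.2/9.6 points. That dilution lowers both tests.

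**4. If pain really is 0.31 v 0.15 overall.** With placebo 0.30 to 0.35 in pain-free eyes, power is 99.1% by chi-square and 99.2–99.7% by CMH.

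**5. The downside.** With two strata and a grade that predicts nothing, the largest loss seen was about 0.2 point (0.35 v 0.47: 78.3% to 78.1%). Six separate grades lost up to about 0.6 point, which favours the two-level cut. Very small pain-free strata (2–10% of eyes) lost at most 0.02 point, which is within simulation error. Two-sided type I error of the two-stratum CMH test was 0.050–0.051 in the main null cases. It was 0.049–0.050 with 2% or 5% of Visit 3 grades missing and placed in the grade 1 or higher stratum.

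**The case against.** The strongest reply is that nothing is broken. The chi-square is valid, pre-specified, and the test on which Section 9.2 is powered: "A two group χ^2 test with a 0.05 two-sided significance level will have 99% power". At the power stated for pain, adjustment adds less than 1 point, which is the very reason for leaving the cells test alone. Larger gains need a strongly prognostic grade, and the documents do not say how prognostic it is. Stratifying also leaves pain-free eyes counted as resolved and does not cure dilution. Finally, it changes a primary test after Amendment 05. Section 9.5 refers to a statistical analysis plan whose separate text is not in the document, so a supportive adjusted analysis cannot be ruled out.

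Much of this stands, and it limits the point to efficiency with a gain that may be close to zero. It does not remove it. The comparison with cells fails in two respects: Section 9.2 gives rates for cells and none for pain, and only pain admits eyes already at the success grade. A supportive analysis elsewhere would not alter the primary test in Section 9.1.2. The choice is between a test that uses a baseline value already collected and one that ignores it, with a possible loss of about 0.2 point against a gain of zero to several points.

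**Conclusion.** The point holds as an improvement in efficiency, not as a fault in error control. With a 16-point effect in all eyes and 20–40% of eyes pain-free, the gain is nil if Visit 3 pain is not prognostic, under 1 point if weakly prognostic (0.45 v 0.25), 1 to 2 points at 0.55 v 0.20, and 2 to 4 at 0.70 v 0.15. If pain-free eyes benefit less, it is 1 point or less at 0.45 v 0.25, 1.6 to 3.6 at 0.55 v 0.20, and about 5 to 13 only under the extreme contrast. All of these sizes rest on assumed pain rates and an assumed pain-free share. The more robust findings are that type I error stays at about 5% and that two strata cost no material power.

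**What to change.** In Section 9.1.2, before unmasking:

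- Make the pain primary a two-sided 0.05 Cochran-Mantel-Haenszel test stratified by the study eye's Visit 3 pain grade (0 v 1 or higher). Its place in the hierarchy does not change.
- Place an eye with no Visit 3 pain grade in the grade 1 or higher stratum, so that every randomized subject stays in the ITT test.
- Report the stratum-weighted risk difference with its 95% CI. With 1:1 allocation, Mantel-Haenszel weights stay close to stratum size, so the target remains the overall difference in proportions.
- Keep the plain chi-square as a sensitivity analysis.

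The cells test can stay as it is: no eye enters with cells resolved, and at 99% planned power adjustment could add at most 1 point. As a minor accompanying edit, Section 9.2 should state the pain rates behind its claim of equal power.

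The cost is a small protocol amendment. Section 12.1 applies: "Any modification of study procedures or amendments to the protocol must be approved by the IRB prior to implementation". No extra patients, visits or data are needed. The pain test would no longer be the test on which Section 9.2 bases its power statement, so that section should say so.
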